1.0 Background

Evidence-based diabetes monitoring and preventative services can prevent or delay many costly and highly morbid disease related complications, yet many patients do not receive all clinically-meaningful, evidence-based services. For example, while detecting and treating early diabetic eye disease can reduce the development of severe vision loss by an estimated 60%, approximately 40% of Americans with diabetes do not receive an annual diabetes eye exam. Prior research has demonstrated numerous barriers to the completion of evidence-based diabetes monitoring and preventative services including patient factors (e.g., lack of awareness and limited health literacy) and clinician/system factors (e.g., limited physician time and patient support between visits). Attempts to increase diabetes monitoring and preventative services have had only modest results. To achieve optimal rates of these services, an intervention is urgently needed that improves clinical efficiency by decreasing clinician workload, is appropriate for patients with varying levels of health literacy, and is highly scalable and sustainable. By providing an engaging and convenient means to track and visualize health data, obtain education and guidance, receive notifications, and connect patients and doctors, patient portals offer a promising platform to enhance access to health services while overcoming the limitations of costly and difficult to scale face-to-face interventions.

2.0 Rationale and Specific Aims

Thus, in this study, we will assess the usability and acceptability of a novel patient portal intervention designed in a prior study to: (a) notify patients when selected, clinically meaningful, evidence-based diabetes monitoring & preventative services (e.g., annual diabetes eye exam) become due and provide reminders for timely completion, (b) promote understanding of the importance of these services through literacy sensitive content, and (c) allow patients, when due by evidence-based guidelines, to initiate orders for the care (e.g., pneumococcal vaccination). In addition, we will assess pre-post change on secondary psychosocial outcomes including patient activation.

3.0 Inclusion/Exclusion Criteria

Participants will be eligible if they receive care at a participating VUMC clinic site and they have type 1 or 2 diabetes mellitus (DM), are able to speak and read in English, are ages 18 to 75, have a current MHAV account and reliable access to a mobile device with iOS or android operating system with internet access, and are due for any of the five guideline-based, diabetes monitoring and preventative services (i.e., hemoglobin A1C, urine microalbumin, diabetes eye exam, and/or pneumococcal vaccination).

We will exclude patients with medical conditions that affects their memory or ability to think which may preventing the use of a mobile device, severe difficulty seeing, severe difficulty hearing, a medical condition that make it hard for people to understand what they are saying, as well as pregnant women or women who plan to become pregnant during the study period.

4.0 Enrollment/Randomization

Participants will be able to complete an electronic consent form and enroll online via Research Electronic Data Capture (REDCap™) version 5.0.8.

5.0 Study Procedures

Setting. The study will be performed at Vanderbilt Primary Care One Hundred Oaks – North and South Clinics located within a large ambulatory care facility in Nashville, TN. An EHR (Epic Systems Corp.) stores all clinical data and patients receive access to their clinical data via an integrated and highly-adopted patient web portal, My Health at Vanderbilt (MHAV), that is accessible on desktops and via a native mobile app for iOS and Android mobile operating systems.

Participants and Recruitment. Potential participants will be identified automatically using VUMC's *Subject Locator* to query the EHR for patients with upcoming clinic appointments who meet the discrete inclusion and exclusion criteria. In addition, VUMC population health and quality improvement initiatives have created a report that identifies established patients with diabetes who receive care at the primary care clinics participating in the study and have current diabetes care gaps (e.g., no diabetes eye exam in the last year). These patients are the target population for study (i.e., Vanderbilt primary care patients with diabetes) and as such these patients are potentially eligible to participate in the study. As with *Subject Locator*, with the permission of the clinic director, these patients would be mailed a recruitment letter describing the study and providing contact information for IRB approved study personnel. With approval of the clinic

director, we will send potentially eligible patients a recruitment letter describing the study and providing them with the contact information for IRB-approved study personnel. If after receiving the letter, a patient is interested in the study, they may contact study personnel to learn more and consider participating in the study. The recruitment letter will include a QR code and URL link to a REDCap site where interested patients can check their eligibility for study, review the consent form, and enroll.

Participants will complete an electronic consent form and enroll online via Research Electronic Data Capture (REDCap™) version 5.0.8. Our target enrollment is 60 participants. In accordance with best practices and to reflect groups with distinct usability needs, we will purposively sample to achieve representation of each of the following characteristics: (a) limited health literacy and (b) age over 65. Some participants may have one or more of these characteristics.

Intervention. The intervention involves the addition of a new feature to the Vanderbilt patient portal that will allow patients to use the My Health at Vanderbilt (MHAV) app on their mobile device (smartphone or tablet) to: (1) receive notifications when they are due for certain types of diabetes monitoring and preventative care and (2) initiate an order for the care. Automated notifications will be sent to patients if, according to the Health Maintenance section of their electronic health record and medical guidelines, they are due for a hemoglobin A1C blood test, microalbumin (kidney) urine test, diabetes eye exam, and/or pneumonia vaccine. If a patient receives a notification, the patient can initiate an order for the care using the MHAV app. After the patient initiates the order, the study team will process the order. Daily, the study team will use Epic's reporting workbench to identify patients that initiated orders and use the EHR's batch order functionality to generate the actual order for the patient's care (e.g., HgbA1c lab test). The patient will receive confirmation when the order has been processed and instructions to proceed to a Vanderbilt clinic or lab to receive the care. The patient's primary care physician will be the authorizing provider and once the patient receives the care, their primary care doctor will receive any results. If the patient has already received the care outside of Vanderbilt, the patient will be able to indicate this. For example, if according to the patient's Vanderbilt medical record they are due for a diabetes eye exam, they will receive a notification; however if they recently had a diabetes eye exam with an eye doctor outside of Vanderbilt, they will be able to report this using the same new MHAV feature.

Patients reporting an outside eye exam will be contacted by study staff and asked to complete an Authorization for Release of Medical Information to VUMC via REDCap. If the patient agrees and signs the release, trained study staff will request the records accordingly. Once the eye exam records are received, trained study staff will review the records to determine if the records document screening for diabetic eye disease (i.e., was the participant's self-report of a diabetes eye exam accurate). If the eye exam records do not indicate screening for diabetes related eye disease (i.e., a diabetes eye exam), KSP will contact the participant by phone with this information and encourage the participant to call their eye doctor to schedule a diabetes eye exam. If the participant prefers, the participant will be invited to schedule a diabetes eye exam at Vanderbilt Eye Institute. If the participant can't be reached by phone, they will be sent a letter with this information. Any outside eye exam records received will be scanned into the participant's VUMC medical record and their primary care physician will be notified.

Data Collection and Outcome Measures. Study participants will complete questionnaires electronically via email using REDCap™ at three time points: enrollment (T_0), after first use of the intervention (T_1), and end of study (T_2). Participants will complete an enrollment questionnaire (T_0) including basic demographic questions, items about computer and internet use, and eHealth literacy. Based on prior experience, we estimate time to completion for each questionnaire to be about 20 minutes. Participants will be compensated \$30 each for completing questionnaires (\$90 total if they complete all three). In addition, participants can receive \$10 for using the intervention for the first time.

The primary outcome measures (**Table 1**) will be: (a) ease of use and satisfaction as assessed by the System Usability Scale at T_1 , (b) system usage data as assessed by user analytics at T_2 , (c) user experience as assessed by 'after first use' and final questionnaires and semi-structured interviews at T_2 . In addition, we will assess pre/post change in the following secondary psychosocial outcomes (**Table 1**) to estimate effect size and standard deviations for power analyses necessary to plan a subsequent randomized controlled trial to be proposed in a subsequent IRB application.

Table 1. Outcome Measures

Primary Outcomes	Measures	Variable Type	How Collected	Time Point
Usability	System Usability Scale (SUS)	Continuous	Questionnaire	T ₁
User experience	Unique study specific items to assess participants' perspectives on content, acceptance, and features and functionality	Categorical	Questionnaire & Interviews	T ₁ and T ₂
Secondary Outcomes	Measures	Variable Type	How Collected	Time Point
Diabetes self-efficacy	Manage Disease in General Scale of the Chronic Disease Self-Efficacy Scales	Continuous	Questionnaire	T ₀ – T ₂
Understanding of Diabetes Monitoring and Preventative Care	Unique study specific items to assess participants' understanding of recommended diabetes monitoring and preventative care	Continuous	Questionnaire	T ₀ – T ₂
Diabetes distress	Problem Areas in Diabetes Scale (PAID-5)	Continuous	Questionnaire	T ₀ – T ₂
Patient-initiated orders	# of patient-initiated orders for evidence-based diabetes monitoring & preventative services (e.g., A1c)	Continuous	EHR Abstraction, Tableau & Clarity Servers	T ₂
Service completion	# of completed (i.e., care received) patient-initiated orders for evidence-based diabetes monitoring & preventative services (e.g., A1c)	Continuous	EHR Abstraction, Tableau & Clarity Servers	T ₂

T₀ = baseline, T₁ = after first use of the intervention, T₂ = 3-month follow up

At the conclusion of their 3-months of access to the intervention, we will conduct one-on-one, semi-structured interviews with a subsample of at least ten participants including at least two participants from each of the purposively sampled groups (**see Recruitment above**). In addition, we will conduct semi structured interviews with up to five primary care physicians (PCPs) that cosigned a patient-initiated order to under their perceptions of the intervention and impacts on workflows. This methodology is most appropriate for in-depth assessment of individuals' perceptions and reactions regarding the intervention. Interviews are preferred over focus groups for understanding usability because focus groups can amplify bias and individual opinions. Participant interviews will take place by phone or via Zoom within two weeks of participants concluding their 3 months of access to the intervention and will last approximately 30 minutes. PCP interviews will take place after all participants have completed the study. A trained interviewer will use a semi-structured interview guide to facilitate the interviews and elicit in-depth understanding of individuals' perceptions and experiences with the intervention. Additional participants will be interviewed until saturation is reached. Saturation will be defined as no new usability concerns raised in the preceding two interviews and typically occurs between 10 and 30 interviews. Interviewees will be compensated \$40 for their time.

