6.0 Statistical Analysis Plan

We will use descriptive statistics to characterize the study participants and survey data. We will use a one sample t-test to compare the mean SUS score at T1 to the threshold score of 71 indicative of "good" usability. To assess whether there was a significant improvement in the continuous secondary cognitive/behavioral outcomes from baseline to end of study (T0 to T1), we will perform two-sided paired t-tests on the pairwise differences. If any of the distributions of pairwise differences suggest asymmetry or nonnormality, the non-parametric Wilcoxon signed-rank test will be performed in lieu of paired t-tests. We will use the McNemar's test for to compare paired proportions. Our primary outcome will be System Usability Scale (SUS) score at first use (T1).

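### Does testing one pooled SUS mean against 71 fail the two groups sampled for their differing usability needs?

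*Combined protocol and SAP*

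**What the plan says.** Section 5.0 (Participants and Recruitment) sets a target of 60 and gives the reason for purposive sampling: "to reflect groups with distinct usability needs, we will purposively sample to achieve representation of each of the following characteristics". The two characteristics are limited health literacy and age over 65. No share is fixed for either, and they may overlap: "Some participants may have one or more of these characteristics".

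Section 6.0 names SUS at T1 as the primary outcome and gives it one specific analysis: "We will use a one sample t-test to compare the mean SUS score at T1 to the threshold score of 71". The same section opens with a general commitment: "We will use descriptive statistics to characterize the study participants and survey data".

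The groups reappear in the interview paragraph of Section 5.0, which refers back to recruitment and requires "at least ten participants including at least two participants from each of the purposively sampled groups". Interviews then continue until the preceding two raise no new usability concern. Section 5.0 and Table 1 list user experience among the primary outcomes, with interviews as one of its sources.

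**The concern.** The protocol says that these two groups differ on the very thing SUS measures, recruits them deliberately, and then averages them with everyone else. With no fixed share, the pooled mean depends on who happens to enrol. It could exceed 71 while one of the groups averages below it, and a reader might take the pooled figure as covering everyone. If the plan had promised group results, or if a decision rested on them, the analysis would not answer its own question.

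**Working it through.** The documents give no SD, expected SUS, group share or significance level for SUS, so there is no planned figure to reproduce. The check has two parts.

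**What the sections commit to**

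- *Aim.* Section 2.0 sets out to assess usability and acceptability of the portal feature overall. It states no subgroup objective.
- *Sampling.* Section 5.0 promises that the groups will be represented. It promises no estimate or comparison by group.
- *Use of the groups.* The interview quota is tied to the sampled groups by an explicit cross-reference. Purposive sampling followed by qualitative coverage of each group is a coherent design.
- *Analysis.* SUS is questionnaire data (Table 1), so the descriptive sentence in Section 6.0 covers a breakdown. The age split needs only age, which is an eligibility variable ("are ages 18 to 75").
- *Decision.* No success rule for SUS is stated. Section 5.0 links planning of the later randomized trial to the effect sizes and SDs of the secondary outcomes, not to a SUS result by group.

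**How large the masking could be, on assumed inputs**

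Assume a lower group with mean 68 and share p, the rest with mean 78, n = 60, and a 5% test. Section 6.0 states sidedness only for the paired tests ("we will perform two-sided paired t-tests on the pairwise differences"), so both versions are shown.

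Pooled mean = 68p + 78(1 − p):

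- p = 0.25: 17.0 + 58.5 = 75.5
- p = 0.40: 27.2 + 46.8 = 74.0

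Lower limit = pooled mean − t × SD/√60, with t = 2.001 (two-sided) or 1.671 (one-sided):

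| Total SD | Two-sided, p = 0.25 → 0.40 | One-sided, p = 0.25 → 0.40 |
|---|---|---|
| 12 | 72.4 → 70.9 | 72.9 → 71.4 |
| 15 | 71.6 → 70.1 | 72.3 → 70.8 |
| 20 | 70.3 → 68.8 | 71.2 → 69.7 |

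Four of the six cells cross 71 and two do not. The answer depends on the SD and sidedness chosen, and the assumed 10-point gap drives all of it. The model also has one lower group against the rest, whereas the plan has two overlapping groups, so it matches neither actual contrast exactly.

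**What a group table would show**

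For a group of 15, the 95% half-width is 2.145 × SD/√15 = 6.65, 8.31 or 11.08 for SD 12, 15 or 20. Around a group mean of 68 this gives:

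- SD 12: 61.4 to 74.6
- SD 15: 59.7 to 76.3
- SD 20: 56.9 to 79.1

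Every interval contains 71. Here SD is the within-group SD, while the table above uses the total SD. Putting both on one basis changes little: a total SD of 15 at p = 0.25 implies a within-group SD of √(225 − 100 × 0.25 × 0.75) = 14.4, and a half-width of about 8.0 instead of 8.3.

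**The case for a change.** The best argument is that the plan itself, not an outside reader, says the groups differ in usability, and Section 1.0 calls for an intervention suited to varying health literacy. Allowing a breakdown is not committing to one. Interviews are qualitative, come at the end of access, and have a floor of two per group, so they do not give the groups' T1 scores. Masking can also be marked: if 15 of 60 averaged 65 and the other 45 averaged 80, the pooled mean would be (15 × 65 + 45 × 80)/60 = 76.25. Against 71 that gives t = 5.25/(SD/√60) = 3.39, 2.54 or 2.03 at SD 12, 16 or 20, each above the critical value of about 2.00, with the group 6 points short.

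The arithmetic is right, and it is true that no group SUS table is pre-specified. But the same illustration can be built for any single-sample mean, and nothing in the documents makes these group means likely. Pre-specification also matters least for a table with no test and no pass rule, since no error rate is at stake.

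One detail does stand. No measure or cut-off for limited health literacy is named; the enrollment questionnaire is described as "including basic demographic questions, items about computer and internet use, and eHealth literacy". That list is introduced as a partial one, so other items may be collected. The missing definition bears on recruitment and on the interview quota, whether or not SUS is tabulated by group. It does not make the SUS analysis wrong.

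**Conclusion.** The concern does not hold. The pooled one-sample t-test is a valid comparison of the recruited sample's mean with 71, the sampled groups have a planned use in the interviews, and the descriptive analysis leaves room for a breakdown. No stated result or decision would change if a group table were added. In the illustrated case of 15 people averaging 68, such a table would leave the group's position against 71 open at every SD tried. The 1.5-point shift in the pooled mean, and whether the lower limit crosses 71, rest on assumed group means, SDs, shares and test level, none of which the documents supply. The conclusion itself rests on two features of the text: the sampling aims at representation only, and no success rule is attached to SUS. If the sponsor later claimed adequate usability for either group on the strength of the pooled mean, that claim would go beyond this plan.

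### The single-group pre/post change is meant to supply the effect size for a later randomized trial, but it does not estimate a between-arm difference, and the SAP does not commit to the SD of change, the T0–T2 correlation or a confidence interval

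*Combined protocol and SAP*

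**What the plan says.** Section 5.0 (Data Collection and Outcome Measures) states that "we will assess pre/post change in the following secondary psychosocial outcomes" and gives the reason: "to estimate effect size and standard deviations for power analyses necessary to plan a subsequent randomized controlled trial". The later trial is left to a separate IRB application. In Table 1 the outcomes measured at both T0 and T2 are diabetes self-efficacy, understanding of monitoring and preventative care (study-specific items) and diabetes distress (PAID-5). Patient-initiated orders and service completion are measured at T2 only.

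No control group or allocation is described. Section 4.0, despite the word Randomization in its title, covers only consent and enrollment: "Participants will be able to complete an electronic consent form and enroll online". On size, Section 5.0 says "Our target enrollment is 60 participants", with no calculation.

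Section 6.0 opens with "We will use descriptive statistics to characterize the study participants and survey data". For the change in the continuous secondary outcomes it says "we will perform two-sided paired t-tests on the pairwise differences"; if the differences look asymmetric or non-normal, "the non-parametric Wilcoxon signed-rank test will be performed in lieu of paired t-tests". It labels the baseline-to-end-of-study interval T0 to T1, whereas Table 1 gives T0 to T2 and defines T1 as after first use.

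**The concern.** A parallel-group trial is powered on the difference between arms. A single-group change equals that difference only if untreated patients would not have changed over the same 3 months. Three features of this study make that doubtful:

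- **Repeat questioning.** The same participants answer at T0 and T2. The understanding items are the most exposed, because being asked about recommended care can itself teach it.
- **Usual care.** One recruitment route is to "query the EHR for patients with upcoming clinic appointments", so ordinary clinic contact may fall inside the follow-up window for those participants.
- **Time trend.** Nothing in the design separates change over 3 months from change due to the portal.

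Supplying planning figures is a stated purpose of this study, so the matter cannot simply be left to the later application. If the mean change is carried forward as the effect size, the later trial could be mis-sized. A pilot of this kind can properly supply the SDs and the T0–T2 correlation, and the second of these has no analysis specified.

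**Working it through.** The documents give no alpha, power, effect size, SD or expected control-group change for either study, so there is no planned figure to reproduce. What follows is an illustration.

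**Inputs.** From the documents: one group, n = 60, T0 and T2 three months apart. Assumed: two-sided alpha 0.05, 80% power, 1:1 allocation, SD 1 in each arm, and a pre/post change of 0.4 between-person SD. Let f be the share of that change that a control group would also show. The true between-arm effect is then d = 0.4 × (1 − f).

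**Size of the later trial.** By the normal approximation, n per arm = 2(1.960 + 0.842)² / d² = 15.70 / d². For d = 0.4 this is 98.1, so 99; the two-sample t calculation gives 100. The t-based results, with power taken at 100 per arm, are:

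| f | True d | Power at 100 per arm | Needed per arm |
|---|---|---|---|
| −25% (controls worsen) | 0.5 | 94% | 64 |
| 0 | 0.4 | 80% | 100 |
| 25% | 0.3 | 56% | 176 |
| 50% | 0.2 | 29% | 394 |

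Sharing a quarter to a half of the change multiplies the required size by about 1.8 to 3.9.

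**Precision with 60 complete pairs.** For a change standardized by the SD of change, the 95% half-width is 1.96 × √(1/n + d²/(2n)). At d = 0.4 this is 1.96 × √(1/60 + 0.16/120) = 0.26. On the between-person scale, 2(1 − r)/n replaces 1/n, where r is the T0–T2 correlation. The half-width is then 0.31 at r = 0.3, 0.26 at r = 0.5 and 0.21 at r = 0.7. An SD has 95% limits of √(59/82.12) = 0.85 and √(59/39.66) = 1.22 times its estimate. So the SD is estimated usably and the effect size poorly, even before any bias.

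**Why the correlation is needed.** A paired t-test works on the scale of the SD of change. With equal SDs at both times, SD of change / SD = √(2(1 − r)). A change of 0.4 between-person SD then becomes 0.4 / √(2(1 − r)):

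- r = 0.3: 0.34, which would suggest 139 per arm if used as a between-arm effect.
- r = 0.5: 0.40, or 100 per arm.
- r = 0.7: 0.52, or 60 per arm.

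Separate T0 and T2 summaries do not give r, so they do not allow conversion between the two scales.

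**The case against.** The strongest reply is that the plan is less bare than a quick reading suggests. A reader might infer that Section 6.0 yields only p-values. It does not: descriptive statistics of the survey data are promised, the three scales are survey data, and SDs at each time point would ordinarily follow. Section 5.0 itself commits to SDs, and a paired t-test computes the SD of the differences. That stands. What remains is that the SD of change, the correlation and a confidence interval are not named as outputs, and the Wilcoxon fallback does not produce them.

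A reader might also infer that the later trial would be undersized by an inflated effect. The documents do not support that. They give no control-group trend, and the table above runs from no loss of power to an oversized trial. Nor do they support two tempting explanations. Regression to the mean would need selection on these scores or on something correlated with them, but Section 3.0 selects on being due for a service. And nothing shows how many participants are recruited around a visit: Section 5.0 has a second route, a care-gap report, and gives no split.

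Finally, it is fair to say that the later trial's target difference and any margin on its SD belong to its own application. This protocol should not be asked to fix them.

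**Conclusion.** The point holds in a limited form. Section 5.0 assigns the single-group change a use for which it is not fit, and Section 6.0 leaves part of the planning aim without a specified analysis. The consequence for the later trial is possible rather than certain. The power figures of 80%, 56% and 29% rest on an assumed change of 0.4 SD and assumed control shares of 0, 25% and 50%; with a worsening control group the error runs the other way. The T0–T1 versus T0–T2 mismatch adds to the problem, because it decides which change and which SD are estimated. The primary analysis of the SUS score at first use is not affected. The change is worth making but does not bear on the validity of the main result.

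**What to change.** **Section 5.0.** Restrict the planning purpose of the secondary psychosocial outcomes to estimating SDs and the T0–T2 correlation. State that the single-group mean change will not be used as the between-arm effect size. Leave the later trial's target difference to its own application.

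**Section 6.0.** For each T0–T2 outcome, commit to reporting the mean change with its 95% CI, the SD at T0 and at T2, the SD of change and the T0–T2 correlation, whichever test is used. Reconcile the interval now labelled T0 to T1 with the T0–T2 interval in Table 1.

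**Cost.** A few sentences and some summary statistics from data already being collected. The small downside is that this study will no longer supply an effect size for the later trial, which may turn out to need more patients.
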